10.6. Appendix 6: Liver Safety: Suggested Actions and Follow-up Assessments

Potential Cases of Drug-Induced Liver Injury

Humans exposed to a drug who show no sign of liver injury (as determined by elevations in transaminases) are termed “tolerators,” while those who show transient liver injury, but adapt are termed “adaptors.” In some participants, transaminase elevations are a harbinger of a more serious potential outcome. These participants fail to adapt and therefore are “susceptible” to progressive and serious liver injury, commonly referred to as drug-induced liver injury (DILI). Participants who experience a transaminase elevation above 3 times the upper limit of normal (\times ULN) should be monitored more frequently to determine if they are an “adaptor” or are “susceptible.”

In the majority of DILI cases, elevations in aspartate aminotransferase (AST) and/or alanine aminotransferase (ALT) precede total bilirubin (TBili) elevations ($>2 \times$ ULN) by several days or weeks. The increase in TBili typically occurs while AST/ALT is/are still elevated above $3 \times$ ULN (ie, AST/ALT and TBili values will be elevated within the same laboratory sample). In rare instances, by the time TBili elevations are detected, AST/ALT values might have decreased. This occurrence is still regarded as a potential DILI. Therefore, abnormal elevations in either AST OR ALT in addition to TBili that meet the criteria outlined below are considered potential DILI (assessed per Hy’s law criteria) cases and should always be considered important medical events, even before all other possible causes of liver injury have been excluded.

The threshold of laboratory abnormalities for a potential DILI case depends on the participant’s individual baseline values and underlying conditions. Participants who present with the following laboratory abnormalities should be evaluated further as potential DILI (Hy’s law) cases to definitively determine the etiology of the abnormal laboratory values:

- Participants with AST/ALT and TBili baseline values within the normal range who subsequently present with AST OR ALT values $>3 \times$ ULN AND a TBili value $>2 \times$ ULN with no evidence of hemolysis and an alkaline phosphatase value $<2 \times$ ULN or not available.
- For participants with baseline AST OR ALT OR TBili values above the ULN, the following threshold values are used in the definition mentioned above, as needed, depending on which values are above the ULN at baseline:
 - Preexisting AST or ALT baseline values above the normal range: AST or ALT values >2 times the baseline values AND $>3 \times$ ULN; or $>8 \times$ ULN (whichever is smaller).
 - Preexisting values of TBili above the normal range: TBili level increased from baseline value by an amount of at least $1 \times$ ULN or if the value reaches $>3 \times$ ULN (whichever is smaller).

Rises in AST/ALT and TBili separated by more than a few weeks should be assessed individually based on clinical judgment; any case where uncertainty remains as to whether it represents a potential Hy's law case should be reviewed with the sponsor.

The participant should return to the investigator site and be evaluated as soon as possible, preferably within 48 hours from awareness of the abnormal results. This evaluation should include laboratory tests, detailed history, and physical assessment.

In addition to repeating measurements of AST and ALT and TBili for suspected cases of Hy's law, additional laboratory tests should include albumin, creatine kinase (CK), direct and indirect bilirubin, gamma-glutamyl transferase (GGT), prothrombin time (PT)/international normalized ratio (INR), total bile acids, and alkaline phosphatase. Consideration should also be given to drawing a separate tube of clotted blood and an anticoagulated tube of blood for further testing, as needed, for further contemporaneous analyses at the time of the recognized initial abnormalities to determine etiology. A detailed history, including relevant information, such as review of ethanol, acetaminophen (either by itself or as a coformulated product in prescription or over-the-counter medications), recreational drug, supplement (herbal) use and consumption, family history, sexual history, travel history, history of contact with a jaundiced person, surgery, blood transfusion, history of liver or allergic disease, and potential occupational exposure to chemicals, should be collected. Further testing for acute hepatitis A, B, C, D, and E infection and liver imaging (eg, biliary tract) and collection of serum sample for acetaminophen drug and/or protein adduct levels may be warranted.

All cases demonstrated on repeat testing as meeting the laboratory criteria of AST/ALT and TBili elevation defined above should be considered potential DILI (Hy's law) cases if no other reason for the liver function test (LFT) abnormalities has yet been found. Such potential DILI (Hy's law) cases are to be reported as SAEs, irrespective of availability of all the results of the investigations performed to determine etiology of the LFT abnormalities.

A potential DILI (Hy's law) case becomes a confirmed case only after all results of reasonable investigations have been received and have excluded an alternative etiology.

10.7. Appendix 7: ECG Findings of Potential Clinical Concern

ECG Findings That May Qualify as Adverse Events (AEs)

- Marked sinus bradycardia (rate <40 beats per minute (bpm)) lasting minutes.
- New PR interval prolongation >280 msec.
- New prolongation of QTcF to >480 msec (absolute) or by ≥ 60 msec from baseline.
- New-onset atrial flutter or fibrillation, with controlled ventricular response rate: ie, rate <120 bpm.
- New-onset type I second-degree (Wenckebach) AV block of >30 seconds' duration.
- Frequent premature ventricular contraction/complexes [per Abbreviations] (PVCs), triplets, or short intervals (<30 seconds) of consecutive ventricular complexes.

ECG Findings That May Qualify as Serious Adverse Events (SAEs)

- QTcF prolongation >500 msec.
- New ST-T changes suggestive of myocardial ischemia.
- New-onset left bundle branch block (QRS >120 msec).
- New-onset right bundle branch block (QRS >120 msec).
- Symptomatic bradycardia.
- Asystole:
 - In awake, symptom-free patients in sinus rhythm, with documented periods of asystole ≥ 3.0 seconds or any escape rate <40 bpm, or with an escape rhythm that is below the AV node;
 - In awake, symptom-free patients with atrial fibrillation and bradycardia with 1 or more pauses of at least 5 seconds or longer;
 - Atrial flutter or fibrillation, with rapid ventricular response rate: rapid = rate >120 bpm.
- Sustained supraventricular tachycardia (rate >120 bpm) ("sustained" = short duration with relevant symptoms or lasting >1 minute).
- Ventricular rhythms >30 seconds' duration, including idioventricular rhythm (rate <40 bpm), accelerated idioventricular rhythm ($40 < x < 100$), and

monomorphic/polymorphic ventricular tachycardia >100 bpm (such as torsades de pointes).
 
• Type II second-degree (Mobitz II) AV block.• Complete (third-degree) heart block.
ECG Findings That Qualify as Serious Adverse Events

• Change in pattern suggestive of new myocardial infarction.• Sustained ventricular tachyarrhythmias (>30 seconds' duration).• Second- or third-degree AV block requiring pacemaker placement.• Asystolic pauses requiring pacemaker placement.• Atrial flutter or fibrillation with rapid ventricular response requiring cardioversion.• Ventricular fibrillation/flutter.• At the discretion of the investigator, any arrhythmia classified as an adverse experience.

The enumerated list of major events of potential clinical concern are recommended as “alerts” or notifications from the core ECG laboratory to the investigator and Pfizer study team, and not to be considered as all inclusive of what to be reported as AEs/SAEs.

10.8. Appendix 8: Prohibited Concomitant Medications

This is not an all-inclusive list. Study personnel should stay current and consult with their pharmacy to exclude all concomitant medications that fall into the categories in the list below:

CYP1A2, CYP3A4, CYP2D6
Inhibitors (Moderate to Strong)

CYP 1A2
Ciprofloxacin
Clinafloxacin
Enoxacin
Fluvoxamine
Oltipraz
Rofecoxib
Zafirlukast

Etintidine
Idrocilamide
Methoxsalen
Mexiletine

Phenylpropanolamine
Pipemidic acid
Propafenone
Propranolol
Troleandomycin
Vemurafenib

CYP 2D6
Quinidine
Fluoxetine
Dacomitinib
Paroxetine
Bupropion

Cinacalcet
Terbinafine
Tipranavir
Moclobemide
Rolapitant
Mirabegron
Duloxetine
Eliglustat
Dronedarone

CYP1A2, CYP3A4,
Inducers (Moderate to
Strong)

CYP 1A2
Phenytoin
Rifampin
Ritonavir
Teriflunomide

MATE substrates
with Narrow
Therapeutic Index

Dofetilide

CYP1A2, CYP3A4, CYP2D6
Inhibitors (Moderate to Strong)

CYP3A4
Viekira pak
Indinavir
Tipranavir
Ritonavir
Cobicistat
Amiodarone
Ketoconazole
Troleandomycin
Telaprevir
Danoprevir
Elvitegravir
Saquinavir
Lopinavir
Itraconazole
Voriconazole
Mibefradil
Clarithromycin
Posaconazole
Telithromycin
Grapefruit Juice***, Marmalade
Conivaptan
Nefazodone
Nelfinavir
Saquinavir
Idelalisib
Boceprevir

Erythromycin
Fluconazole
Atazanavir
Darunavir
Diltiazem
Dronedarone
Crizotinib
Aprepitant
Casopitant
Amprenavir
Faldaprevir
Imatinib
Verapamil
Netupitant

CYP1A2, CYP3A4,
Inducers (Moderate to
Strong)

CYP3A4
Rifampin
Mitotane
Avasimibe
Phenytoin
Carbamazepine

Enzalutamide
St. John's wort
Rifabutin
Phenobarbital

Semagacestat
Efavirenz
Bosentan
Genistein
Thioridazine
Nafcillin
Talviraline
Lopinavir
Modafanil
Etravirine
Lersivirine

MATE substrates
with Narrow
Therapeutic Index

CYP1A2, CYP3A4, CYP2D6
Inhibitors (Moderate to Strong)

CYP1A2, CYP3A4,
Inducers (Moderate to
Strong)

MATE substrates
with Narrow
Therapeutic Index

Nilotinib
Tofisopam
Cyclosporine
Ciprofloxacin
Isavuconazole
Cimetidine

- All prohibited drugs that are CYP1A2, CYP3A and CYP2D6 inhibitors require at least a 7 day or 5 half-lives (whichever is longer) prior to the first dose of study drug. Note: Amiodarone requires discontinuation at least 290 days (~5 half-lives, half-life averages ~58 days) prior to the first dose of IP.
- All prohibited drugs that are CYP1A2 and CYP3A inducers require at least a 28 day or 5 half-lives (whichever is longer) prior to the first dose of IP.
- ***It is recommended that subjects avoid excessive consumption of grapefruit juice exceeding 8 ounces (~240 mL) total in a day while in the study.
- **In a situation where appropriate medical care of a subject requires the use of a prohibited inhibitor or inducer:**

Moderate to potent inhibitors of CYP1A2, CYP3A and CYP2D6 and inducers of CYP1A2 and CYP3A are not permitted in the study EXCEPT in emergency situations requiring no more than one day of administration. **Note: Amiodarone and mitotane are not permitted for any duration due to their long half-lives.** Topical (including skin or mucous membranes) application of antimicrobial and antifungal medications is permitted.

10.9. Appendix 9: Columbia Suicide Severity Rating Scale (C-SSRS) for Screening and Baseline Visit

SUICIDAL IDEATION		
Ask questions 1 and 2. If both are negative, proceed to "Suicidal Behavior" section. If the answer to question 2 is "yes", ask questions 3, 4 and 5. If the answer to question 1 and/or 2 is "yes", complete "Intensity of Ideation" section below.	Lifetime: Time He/She Felt Most Suicidal	Past ___ Months
1. Wish to be Dead Subject endorses thoughts about a wish to be dead or not alive anymore, or wish to fall asleep and not wake up. Have you wished you were dead or wished you could go to sleep and not wake up? If yes, describe:	Yes No  	Yes No  
2. Non-Specific Active Suicidal Thoughts General non-specific thoughts of wanting to end one's life/commit suicide (e.g., "I've thought about killing myself") without thoughts of ways to kill oneself/associated methods, intent, or plan during the assessment period. Have you actually had any thoughts of killing yourself? If yes, describe:	Yes No  	Yes No  
3. Active Suicidal Ideation with Any Methods (Not Plan) without Intent to Act Subject endorses thoughts of suicide and has thought of at least one method during the assessment period. This is different than a specific plan with time, place or method details worked out (e.g. thought of method to kill self but not a specific plan). Includes person who would say, "I thought about taking an overdose but I never made a specific plan as to when, where or how I would actually do it...and I would never go through with it." Have you been thinking about how you might do this? If yes, describe:	Yes No  	Yes No  
4. Active Suicidal Ideation with Some Intent to Act, without Specific Plan Active suicidal thoughts of killing oneself and subject reports having some intent to act on such thoughts , as opposed to "I have the thoughts but I definitely will not do anything about them." Have you had these thoughts and had some intention of acting on them? If yes, describe:	Yes No  	Yes No  
5. Active Suicidal Ideation with Specific Plan and Intent Thoughts of killing oneself with details of plan fully or partially worked out and subject has some intent to carry it out. Have you started to work out or worked out the details of how to kill yourself? Do you intend to carry out this plan? If yes, describe:	Yes No  	Yes No  
INTENSITY OF IDEATION		
The following features should be rated with respect to the most severe type of ideation (i.e., 1-5 from above, with 1 being the least severe and 5 being the most severe). Ask about time he/she was feeling the most suicidal.		
Lifetime - Most Severe Ideation: _____ Type # (1-5) Description of Ideation	Most Severe	Most Severe
Past X Months - Most Severe Ideation: _____ Type # (1-5) Description of Ideation		
Frequency How many times have you had these thoughts? (1) Less than once a week (2) Once a week (3) 2-5 times in week (4) Daily or almost daily (5) Many times each day	—	—
Duration When you have the thoughts how long do they last? (1) Fleeting - few seconds or minutes (4) 4-8 hours/most of day (2) Less than 1 hour/some of the time (5) More than 8 hours/persistent or continuous (3) 1-4 hours/a lot of time	—	—
Controllability Could/can you stop thinking about killing yourself or wanting to die if you want to? (1) Easily able to control thoughts (4) Can control thoughts with a lot of difficulty (2) Can control thoughts with little difficulty (5) Unable to control thoughts (3) Can control thoughts with some difficulty (0) Does not attempt to control thoughts	—	—
Deterrents Are there things - anyone or anything (e.g., family, religion, pain of death) - that stopped you from wanting to die or acting on thoughts of committing suicide? (1) Deterrents definitely stopped you from attempting suicide (4) Deterrents most likely did not stop you (2) Deterrents probably stopped you (5) Deterrents definitely did not stop you (3) Uncertain that deterrents stopped you (0) Does not apply	—	—
Reasons for Ideation What sort of reasons did you have for thinking about wanting to die or killing yourself? Was it to end the pain or stop the way you were feeling (in other words you couldn't go on living with this pain or how you were feeling) or was it to get attention, revenge or a reaction from others? Or both? (1) Completely to get attention, revenge or a reaction from others (4) Mostly to end or stop the pain (you couldn't go on living with the pain or how you were feeling) (2) Mostly to get attention, revenge or a reaction from others (5) Completely to end or stop the pain (you couldn't go on living with the pain or how you were feeling) (3) Equally to get attention, revenge or a reaction from others and to end/stop the pain (0) Does not apply	—	—

SUICIDAL BEHAVIOR (Check all that apply, so long as these are separate events; must ask about all types)		Lifetime		Past   Years	
Actual Attempt: A potentially self-injurious act committed with at least some wish to die, as a result of act . Behavior was in part thought of as method to kill oneself. Intent does not have to be 100%. If there is any intent/desire to die associated with the act, then it can be considered an actual suicide attempt. There does not have to be any injury or harm , just the potential for injury or harm. If person pulls trigger while gun is in mouth but gun is broken so no injury results, this is considered an attempt. Inferring Intent: Even if an individual denies intent/wish to die, it may be inferred clinically from the behavior or circumstances. For example, a highly lethal act that is clearly not an accident so no other intent but suicide can be inferred (e.g., gunshot to head, jumping from window of a high floor/story). Also, if someone denies intent to die, but they thought that what they did could be lethal, intent may be inferred. Have you made a suicide attempt? Have you done anything to harm yourself? Have you done anything dangerous where you could have died? What did you do? Did you _____ as a way to end your life? Did you want to die (even a little) when you _____? Were you trying to end your life when you _____? Or Did you think it was possible you could have died from _____? Or did you do it purely for other reasons / without ANY intention of killing yourself (like to relieve stress, feel better, get sympathy, or get something else to happen)? (Self-Injurious Behavior without suicidal intent) If yes, describe:		Yes No   Total # of Attempts _____	Yes No   Total # of Attempts _____		
Has subject engaged in Non-Suicidal Self-Injurious Behavior?		Yes No  	Yes No  		
Interrupted Attempt: When the person is interrupted (by an outside circumstance) from starting the potentially self-injurious act (if not for that, actual attempt would have occurred). Overdose: Person has pills in hand but is stopped from ingesting. Once they ingest any pills, this becomes an attempt rather than an interrupted attempt. Shooting: Person has gun pointed toward self, gun is taken away by someone else, or is somehow prevented from pulling trigger. Once they pull the trigger, even if the gun fails to fire, it is an attempt. Jumping: Person is poised to jump, is grabbed and taken down from ledge. Hanging: Person has noose around neck but has not yet started to hang - is stopped from doing so. Has there been a time when you started to do something to end your life but someone or something stopped you before you actually did anything? If yes, describe:		Yes No   Total # of interrupted _____	Yes No   Total # of interrupted _____		
Aborted Attempt: When person begins to take steps toward making a suicide attempt, but stops themselves before they actually have engaged in any self-destructive behavior. Examples are similar to interrupted attempts, except that the individual stops him/herself, instead of being stopped by something else. Has there been a time when you started to do something to try to end your life but you stopped yourself before you actually did anything? If yes, describe:		Yes No   Total # of aborted _____	Yes No   Total # of aborted _____		
Preparatory Acts or Behavior: Acts or preparation towards imminently making a suicide attempt. This can include anything beyond a verbalization or thought, such as assembling a specific method (e.g., buying pills, purchasing a gun) or preparing for one's death by suicide (e.g., giving things away, writing a suicide note). Have you taken any steps towards making a suicide attempt or preparing to kill yourself (such as collecting pills, getting a gun, giving valuables away or writing a suicide note)? If yes, describe:		Yes No  	Yes No  		
Suicidal Behavior: Suicidal behavior was present during the assessment period?		Yes No  	Yes No  		
Answer for Actual Attempts Only		Most Recent Attempt Date:	Most Lethal Attempt Date:	Initial/First Attempt Date:	
Actual Lethality/Medical Damage: 0. No physical damage or very minor physical damage (e.g., surface scratches). 1. Minor physical damage (e.g., lethargic speech; first-degree burns; mild bleeding; sprains). 2. Moderate physical damage; medical attention needed (e.g., conscious but sleepy, somewhat responsive; second-degree burns; bleeding of major vessel). 3. Moderately severe physical damage; medical hospitalization and likely intensive care required (e.g., comatose with reflexes intact; third-degree burns less than 20% of body; extensive blood loss but can recover; major fractures). 4. Severe physical damage; medical hospitalization with intensive care required (e.g., comatose without reflexes; third-degree burns over 20% of body; extensive blood loss with unstable vital signs; major damage to a vital area). 5. Death		Enter Code _____	Enter Code _____	Enter Code _____	
Potential Lethality: Only Answer if Actual Lethality=0 Likely lethality of actual attempt if no medical damage (the following examples, while having no actual medical damage, had potential for very serious lethality: put gun in mouth and pulled the trigger but gun fails to fire so no medical damage; laying on train tracks with oncoming train but pulled away before run over). 0 = Behavior not likely to result in injury 1 = Behavior likely to result in injury but not likely to cause death 2 = Behavior likely to result in death despite available medical care		Enter Code _____	Enter Code _____	Enter Code _____	

C-SSRS for any post-baseline visits “since last visit version”:

SUICIDAL IDEATION		Lifetime: Time He/She Felt Most Suicidal		Past ___ Months	
Ask questions 1 and 2. If both are negative, proceed to “Suicidal Behavior” section. If the answer to question 2 is “yes”, ask questions 3, 4 and 5. If the answer to question 1 and/or 2 is “yes”, complete “Intensity of Ideation” section below.					
1. Wish to be Dead Subject endorses thoughts about a wish to be dead or not alive anymore, or wish to fall asleep and not wake up. Have you wished you were dead or wished you could go to sleep and not wake up?		Yes 	No 	Yes 	No 
If yes, describe:					
2. Non-Specific Active Suicidal Thoughts General non-specific thoughts of wanting to end one’s life/commit suicide (e.g., “I’ve thought about killing myself”) without thoughts of ways to kill oneself/associated methods, intent, or plan during the assessment period. Have you actually had any thoughts of killing yourself?		Yes 	No 	Yes 	No 
If yes, describe:					
3. Active Suicidal Ideation with Any Methods (Not Plan) without Intent to Act Subject endorses thoughts of suicide and has thought of at least one method during the assessment period. This is different than a specific plan with time, place or method details worked out (e.g. thought of method to kill self but not a specific plan). Includes person who would say, “I thought about taking an overdose but I never made a specific plan as to when, where or how I would actually do it...and I would never go through with it.” Have you been thinking about how you might do this?		Yes 	No 	Yes 	No 
If yes, describe:					
4. Active Suicidal Ideation with Some Intent to Act, without Specific Plan Active suicidal thoughts of killing oneself and subject reports having some intent to act on such thoughts , as opposed to “I have the thoughts but I definitely will not do anything about them.” Have you had these thoughts and had some intention of acting on them?		Yes 	No 	Yes 	No 
If yes, describe:					
5. Active Suicidal Ideation with Specific Plan and Intent Thoughts of killing oneself with details of plan fully or partially worked out and subject has some intent to carry it out. Have you started to work out or worked out the details of how to kill yourself? Do you intend to carry out this plan?		Yes 	No 	Yes 	No 
If yes, describe:					
INTENSITY OF IDEATION					
The following features should be rated with respect to the most severe type of ideation (i.e., 1-5 from above, with 1 being the least severe and 5 being the most severe). Ask about time he/she was feeling the most suicidal.					
Lifetime - Most Severe Ideation: _____ Type # (1-5) _____ Description of Ideation _____		Most Severe		Most Severe	
Past X Months - Most Severe Ideation: _____ Type # (1-5) _____ Description of Ideation _____					
Frequency How many times have you had these thoughts? (1) Less than once a week (2) Once a week (3) 2-5 times in week (4) Daily or almost daily (5) Many times each day		_____		_____	

SUICIDAL BEHAVIOR (Check all that apply, so long as these are separate events; must ask about all types)		Since Last Visit

Actual Attempt: A potentially self-injurious act committed with at least some wish to die, as a result of act. Behavior was in part thought of as method to kill oneself. Intent does not have to be 100%. If there is any intent/desire to die associated with the act, then it can be considered an actual suicide attempt. There does not have to be any injury or harm, just the potential for injury or harm. If person pulls trigger while gun is in mouth but gun is broken so no injury results, this is considered an attempt. Inferring Intent: Even if an individual denies intent/wish to die, it may be inferred clinically from the behavior or circumstances. For example, a highly lethal act that is clearly not an accident so no other intent but suicide can be inferred (e.g., gunshot to head, jumping from window of a high floor/story). Also, if someone denies intent to die, but they thought that what they did could be lethal, intent may be inferred. Have you made a suicide attempt? Have you done anything to harm yourself? Have you done anything dangerous where you could have died? What did you do? Did you _____ as a way to end your life? Did you want to die (even a little) when you _____? Were you trying to end your life when you _____? Or did you think it was possible you could have died from _____? Or did you do it purely for other reasons / without ANY intention of killing yourself (like to relieve stress, feel better, get sympathy, or get something else to happen)? (Self-Injurious Behavior without suicidal intent) If yes, describe:
	
Yes No  
 
Total # of Attempts _____
 
Yes No  
	

Has subject engaged in Non-Suicidal Self-Injurious Behavior?
	
Yes No  
	

Interrupted Attempt: When the person is interrupted (by an outside circumstance) from starting the potentially self-injurious act (if not for that, actual attempt would have occurred). Overdose: Person has pills in hand but is stopped from ingesting. Once they ingest any pills, this becomes an attempt rather than an interrupted attempt. Shooting: Person has gun pointed toward self, gun is taken away by someone else, or is somehow prevented from pulling trigger. Once they pull the trigger, even if the gun fails to fire, it is an attempt. Jumping: Person is poised to jump, is grabbed and taken down from ledge. Hanging: Person has noose around neck but has not yet started to hang - is stopped from doing so. Has there been a time when you started to do something to end your life but someone or something stopped you before you actually did anything? If yes, describe:
	
Yes No  
 
Total # of interrupted _____
	

Aborted Attempt: When person begins to take steps toward making a suicide attempt, but stops themselves before they actually have engaged in any self-destructive behavior. Examples are similar to interrupted attempts, except that the individual stops him/herself, instead of being stopped by something else. Has there been a time when you started to do something to try to end your life but you stopped yourself before you actually did anything? If yes, describe:
	
Yes No  
 
Total # of aborted _____
	

Preparatory Acts or Behavior: Acts or preparation towards imminently making a suicide attempt. This can include anything beyond a verbalization or thought, such as assembling a specific method (e.g., buying pills, purchasing a gun) or preparing for one's death by suicide (e.g., giving things away, writing a suicide note). Have you taken any steps towards making a suicide attempt or preparing to kill yourself (such as collecting pills, getting a gun, giving valuables away or writing a suicide note)? If yes, describe:
	
Yes No  
	

Suicidal Behavior: Suicidal behavior was present during the assessment period?	Yes No  
Suicide:	Yes No  
Answer for Actual Attempts Only	Most Lethal Attempt Date

Actual Lethality/Medical Damage: 0. No physical damage or very minor physical damage (e.g., surface scratches). 1. Minor physical damage (e.g., lethargic speech; first-degree burns; mild bleeding; sprains). 2. Moderate physical damage; medical attention needed (e.g., conscious but sleepy, somewhat responsive; second-degree burns; bleeding of major vessel). 3. Moderately severe physical damage; medical hospitalization and likely intensive care required (e.g., comatose with reflexes intact; third-degree burns less than 20% of body; extensive blood loss but can recover; major fractures). 4. Severe physical damage; medical hospitalization with intensive care required (e.g., comatose without reflexes; third-degree burns over 20% of body; extensive blood loss with unstable vital signs; major damage to a vital area). 5. Death
	Enter Code _____

Potential Lethality: Only Answer if Actual Lethality=0 Likely lethality of actual attempt if no medical damage (the following examples, while having no actual medical damage, had potential for very serious lethality: put gun in mouth and pulled the trigger but gun fails to fire so no medical damage, laying on train tracks with oncoming train but pulled away before run over). 0 = Behavior not likely to result in injury 1 = Behavior likely to result in injury but not likely to cause death 2 = Behavior likely to result in death despite available medical care
	Enter Code _____

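### The post-baseline C-SSRS form in Protocol Appendix 9 prints lifetime and past-months recall in its ideation and intensity blocks, where the protocol requires recall since the last visit

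*Protocol*

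**What the plan says.** Protocol Section 8.2.5.1 and footnote g of the SoA (Section 1.3) agree on which version of the scale belongs where: lifetime at Screening and Baseline, since last visit thereafter. The SoA schedules two post-baseline administrations, at Weeks 16 and 40.

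Appendix 9 (Section 10.9) prints two forms. The second is titled "C-SSRS for any post-baseline visits" and labelled as the since-last-visit version. Under that title:

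- The ideation block is headed "Lifetime: Time He/She Felt Most Suicidal", next to a column for a blank number of past months. Each of its five items has a Yes/No pair under both columns.
- The intensity block asks for "Lifetime - Most Severe Ideation" and "Past X Months - Most Severe Ideation".
- The behaviour block is headed "Since Last Visit" and has a single answer column.

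Section 8.2.5.1 attaches actions to the answers. A YES on item 4, item 5 or any behaviour question at any visit calls for an immediate risk assessment. After Day 1 it also suspends study drug until the participant has been evaluated. A YES on more than one occasion means discontinuation from the trial.

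At entry, exclusion criterion 5a and Section 8.2.1.4 rule out item 4 or 5 ideation in the past year. Older ideation is excluded only at the discretion of the investigator or sponsor (criteria 5c and 17).

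**The concern.** The form and the rule it serves disagree on the recall period. A since-last-visit instrument exists to capture ideation arising between visits. With lifetime and open-ended past-months columns, no ideation answer on the printed page isolates that interval.

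This matters because items 4 and 5 prompt action. An eligible participant may have had such ideation more than a year before entry. Asked over a lifetime at Week 16, that person can truthfully answer YES with nothing new to report. The answer then meets the literal condition for an assessment and a drug hold, and pre-study ideation could be recorded as an on-treatment finding.

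**Working it through.** No calculation applies. The check sets the two printed forms and the rule side by side.

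**1. Recall by block.**

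| Block | Screening/Baseline form | Post-baseline form | Required post-baseline |
|---|---|---|---|
| Ideation | Lifetime; past months (blank) | Lifetime; past months (blank) | Since last visit |
| Intensity | Lifetime; past X months | Lifetime; past X months | Since last visit |
| Behaviour | Lifetime; past years (blank) | Since last visit | Since last visit |

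Two of three blocks are wrong. Their recall labels are those of the Screening/Baseline form, which suggests a carry-over.

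**2. Could this be an artefact of reading the PDF?** Unlikely. After the post-baseline title, the wrong recall appears in the ideation header, in the two-column answer layout and in both intensity lines. The next block has a different header and a one-column layout. A broken table would not produce that pattern.

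**3. Does the wording of the questions supply the recall period?** Item 3 refers to a participant who "has thought of at least one method during the assessment period", and item 2 uses the same closing phrase. Item 4 asks "Have you had these thoughts and had some intention of acting on them" and item 5 is similar; neither states a period. So 2 of the 5 items carry recall wording (items 2 and 3), and 0 of the 2 ideation items that trigger action do. The behaviour block shows how the form normally works: the question beginning "Has there been a time when you started to do something to end your life" names no period either, and the column header provides it. For items 4 and 5 the header provides the wrong one.

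**4. Trace one participant through the page as printed.**

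- History: item 4 ideation more than one year before entry. Criterion 5a is not met, so the participant can be enrolled unless discretion is used.
- Screening and Baseline: YES under Lifetime, correctly.
- Week 16: YES under Lifetime again, truthfully. What goes under past months depends on a number the form does not fix. Read literally, Section 8.2.5.1 requires a risk assessment and a temporary hold.
- Week 40: the same answer would be a second post-baseline occasion and would meet the discontinuation wording. SAP Appendix 2.1, footnote c, describes Week 40 as the last on-treatment visit, so little or no planned dosing would be lost.

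**5. Completeness of the intensity block.** The Screening/Baseline form lists five features: Frequency, Duration, Controllability, Deterrents and Reasons. In the text available here, the post-baseline block stops after Frequency, 1 of 5. Whether the protocol prints it that way or the PDF conversion lost the rest cannot be told.

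**The case against.** The strongest reply is that the operative instruction is clear: Section 8.2.5.1, footnote g and the form's title all say the same thing. The unfilled month placeholders make the page look like a template, and sites may have used a different form or device. This stands as a limit on the consequence. It does not remove the contradiction, because Appendix 9 is the only post-baseline form in the documents.

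Several features also reduce over-triggering:

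- **The item 2 gate.** Items 3 to 5 are asked only after a YES on item 2, which is tied to the assessment period. This helps, but not conclusively: the Screening/Baseline form uses the same phrase under lifetime columns, so the phrase can take its meaning from the header.
- **Known history.** Old ideation should already be recorded under Lifetime at Screening and Baseline, and the Week 16 evaluator would normally have it.
- **Free text and footnote g.** Each item asks for a description of a YES, and footnote g speaks of recent or active ideation. Both help to separate old from new.
- **The two columns.** They separate lifetime from more recent ideation, but with the number of months blank neither marks the interval since the last visit.

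A reader might infer that everything except the behaviour block was copied unchanged. The text does not support that, because the intensity block also differs in length. A reader might also take this for a flaw in the suicidality monitoring design. It is not: the rule is sound and the specimen form departs from it.

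**Conclusion.** The mismatch is certain from the text: two of the three blocks of the post-baseline form carry the wrong recall, and neither item 4 nor item 5 has wording that corrects it. The severity is minor. Any consequence requires that sites used the page as printed and that enrolled participants had item 4 or 5 ideation more than a year old. The documents give neither the deployed form nor the number of such participants, so no count is offered.

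The likely direction is over-triggering. A reader might infer that new ideation would be missed, but recall over a lifetime includes the interval since the last visit. The weakness is that new ideation cannot be told apart from old.

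A reader might also infer that participants were wrongly stopped or that the primary result is at risk. The documents do not support either. The first scheduled post-baseline C-SSRS is at Week 16, the visit of the PASI 90 endpoint, so a hold prompted by it comes too late to alter that response. The readable endpoint lists in SAP Sections 3.1.2, 3.2.1 and 3.4 do not name the C-SSRS. No efficacy analysis is affected.

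**What to change.** In the post-baseline form of Appendix 9:

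1. Replace the two recall columns of the ideation block with a single since-last-visit column, changing both the header and the answer boxes. The five items then have 5 x 1 = 5 Yes/No answers instead of 5 x 2 = 10.
2. Replace the lifetime and past-months lines of the intensity block with a single since-last-visit line.
3. Check that Duration, Controllability, Deterrents and Reasons are present, and restore them if they are not.
4. Confirm that the form or device build used at sites has the same recall.

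The Screening/Baseline form and the triggers in Section 8.2.5.1 stay as they are. The cost is an edit to one appendix form, in the next amendment or a clarification letter, plus the check of the deployed build. The amendment history shows that a clarification letter was already used for a C-SSRS footnote. No threshold, endpoint or analysis changes.
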